**As OG training covers both obstetrics and gynaecology curriculums, we will recruit trainees in their final two years of training, with gynaecology special interest, who are undertaking at least one gynaecology Advanced Training Skills Modules (ATSM). These include advanced laparoscopic training, open and laparoscopic benign abdomen, urogynaecology, gynaecology-oncology and reproductive medicine. These ATSMs involve core laparoscopic skills such as laparoscopic suturing as an essential component of their curriculum.

Trainees (Exclusion Criteria)

Those trainees who have had substantial pre-training experience in laparoscopic surgery such as those who have completed another surgical speciality training, have worked as clinical fellows or speciality doctor with substantial exposure to laparoscopic work will be excluded. Those trainees who are currently out of program/training and not doing regular clinical work or those trainees outside the North West deanery will also be excluded. For the safety of others anybody with positive Covid-19 test, symptoms or contact with someone infected with the virus will be excluded.

Withdrawal

Participation in this study is voluntary and all participants will be required to provide explicit consent (**Appendix 3 &4**). Participants can withdraw at any time by contacting a member of the research team.

Study Protocol

Part 1 consists of questionnaires sent out to Consultants and trainees.

Consultant Questionnaire (Appendix 1)

A questionnaire will be sent to consultants nationally via the RCOG and BSGE (O&G consultants) and ASGBI (GS consultants) to get an idea of their own level of laparoscopic surgical experience and their expectations of laparoscopic competencies required at CCT by trainees. No personal details will be requested in the questionnaires.

The email accompanying the questionnaires email will contain a brief introduction to the study, a participant information sheet (**Appendix 3**) and consent form (**Appendix 4**) as attachments and a link to the online questionnaire. All questionnaires will be returned anonymously via survey monkey service.

Trainee Questionnaire (Appendix 2)

A short questionnaire will be sent to trainees nationally via the RCOG and BSGE assessing their perception of self rated laparoscopic ability and skills they rate as important at CCT. No personal details will be requested in the questionnaires.

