The email accompanying the questionnaires will contain a brief introduction to the study, a participant information sheet (**Appendix 3**), consent form (**Appendix 4**) as attachments and a link to the online questionnaire.

The completed questionnaires will be returned to us via 'survey monkey' service.

Part 2:

This phase consist of four FLS tasks and EMG/EEG data recording on a randomly selected small subset of trainees.

The relevant trainees (ST3, ST4 , ST5 grades in both specialties, ST6/7 in O&G and ST7/8 in GS) will be identified and approached through north west deanery on our behalf who hold contact details for all trainees in the region. This email will contain a brief introduction to the study and request their help by volunteering with the FLS tasks if they meet the selection criteria. This email will contain a participant information sheet and consent form (Appendix 3 & 5 respectively) as attachments. Trainees will be able to self select from this information if they meet the inclusion criteria and volunteer their help. There will be a secure email address for them to reply to if they wish to volunteer. In addition to above recruitment methods we will consider the use of social media and direct emails to increase trainee recruitment for the study

Volunteering for FLS (part 2) is not contingent on trainees completing the questionnaire in part 1 of study. Trainees can help with both parts of the study or one or the other as they are able.

Trainees volunteering for the FLS tasks will be requested for their preferred contact number or email. This will be used by the research team to verify their inclusion criteria and offer a convenient date from a choice of 6 days over 3 separate weekends for the FLS tasks in part 2. By engaging in this process we are restricting our access to personal details on a strictly 'need to know basis', i.e. only dealing with personal details of trainees interested in volunteering for FLS tasks.

On the day, trainees will be asked to fill out a short questionnaire on demographic details, previous laparoscopic experience, physical fitness and presence of any musculoskeletal symptoms as these are potential confounding variables (**Appendix 6**). A written consent form will be completed at this stage (**Appendix 5**).

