Appendix

- 1. Consultant Questionnaire (Appendix 1)**
- 2. Trainee Questionnaire I (Appendix 2)**
- 3. Participant information sheet (Appendix 3)**
- 4. Consent Form 1 (Appendix 4)**
- 5. Consent form 2 (Appendix 5)**
- 6. Trainee questionnaire II (Appendix 6)**
- 7. Trainee Standardised Task Instructions (Appendix 7)**
- 8. Validated Laparoscopic tasks scoring Form (Appendix 8)**
- 9. Validated suturing scoring system (Appendix 9)**
- 10. EMG will be measured by placing wireless electrodes over arms, neck and back muscles (Appendix 10)**
- 11. EEG will be recorded using wireless electrodes over parietal cortex using validated protocols. (Appendix 11)**
- 12. Equipment (Appendix 12)**
- 13. Assessor Instructions (Appendix 13)**

Appendix 1

Consultant Questionnaire: Expectations of Fundamental Laparoscopic Skills Required by the end of Higher Specialty Training

Gender

	Mark with 'X'		Mark with 'X'
Male		Female	

Please state the year you became a consultant.

Specialty

	Mark with 'X'		Mark with 'X'
General Surgery – Colorectal/HPB/Upper GI		Gynaecology only	
		Obstetrics and gynaecology	

Where did you complete the majority of your higher surgical Training?

	Mark with 'X'
UK	
EU, not UK	
Outside of the EU	

What percentage of your work do you perform laparoscopically?

	Mark with 'X'
0-25%	
25-50%	
50-75%	
75-100%	

What are your expectations of required laparoscopic abilities of trainees at CCT? For gynaecology consultants please base your answers on a trainee who is undertaking the following ATSM: Advanced laparoscopy, open and laparoscopic benign abdomen, gynae-oncology and other sub specialty trainees involving major laparoscopic work. Please mark your answer with an 'X'

Strongly Disagree – 1, Disagree -2, Neither agree nor disagree-3, Agree -4 and Strongly agree – 5.

Laparoscopic ability	1	2	3	4	5
Proficient in obtaining laparoscopic intra-abdominal access					
Proficient in recognition of anatomy and anatomic tissue planes laparoscopically					
Proficient in safe manipulation of tissue laparoscopically					
Proficient in dissection of tissue planes laparoscopically					

Able to control bleeding laparoscopically using diathermy/energy devices.					
Able to control bleeding laparoscopically using endovascular staplers/haemolocks/endoloops					
Able to control bleeding laparoscopically using haemostatic agents ie Flowseal/surgicel					
Proficient in appropriate use of laparoscopic energy devices					
Proficient in laparoscopic suturing					

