Male (including transgender men)		Female (including transgender women)	Other		Prefer not to say	

2. Specialty

	Mark with 'X'		Mark with 'X'
General Surgery – Colorectal/HPB/Upper GI		Other	
Obstetrics and gynaecology			

3. Are you currently enrolled in a specialty training program?

Yes/ No

4. Which deanery are you currently enrolled in a training program in? Please mark your answer with an X.

North East Yorkshire and Humber North west
 East midlands West midlands East of England South West
 Thames valley Wessex Kent/surrey/Sussex (KSS)
 North central and East London North West London
 South London.

5. Which level of training are you currently?

Please mark your answer with an X					
ST3	ST4	ST5	ST6	ST7	ST8

6. When did you commence higher surgical training/Obs and Gynae Training? (Year) _____

7. Please select the NHS deanery in which you are currently employed in. Please mark your answer with an X.

North East Yorkshire and Humber North west
 East midlands West midlands East of England South West
 Thames valley Wessex Kent/surrey/Sussex (KSS)
 North central and East London North West London
 South London. None of the above.

8. What are your **expectations** of required laparoscopic abilities of trainees at CCT? Please mark your answer with an 'X'

Strongly Disagree – 1, Disagree -2, Neither agree nor disagree-3, Agree -4 and Strongly agree – 5.

Laparoscopic ability	1	2	3	4	5
Proficient in obtaining laparoscopic intra-abdominal access					
Proficient in recognition of anatomy and anatomic tissue planes laparoscopically					
Proficient in safe manipulation of tissue laparoscopically					
Proficient in dissection of tissue planes laparoscopically					
Able to control bleeding laparoscopically using diathermy/energy devices.					
Able to control bleeding laparoscopically using endovascular staplers/haemolocks/endoloops					
Able to control bleeding laparoscopically using haemostatic agents ie Flowseal/surgicel					
Proficient in appropriate use of laparoscopic energy devices					
Proficient in laparoscopic suturing					
Proficient in use of laparoscopic staplers					

How would you rate **your own confidence** with the listed laparoscopic skills? Please mark your answer with an 'X'

Not at all confident -1, Not so confident-2, Somewhat confident -3, Very confident -4, extremely confident-5.

Laparoscopic ability	1	2	3	4	5
Proficient in obtaining laparoscopic intra-abdominal access					

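### On the forms, O&G consultants and O&G trainees are asked for their expectations of differently defined trainees, so the O&G consultant-trainee comparison is not like-for-like

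*Protocol*

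**What the plan says.** The Hypothesis section expects consultants and trainees to differ, within both specialties, in the skills they think important at CCT. Two part 1 questionnaires supply the data.

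- **Appendix 1 (consultants).** The expectations question carries an instruction for one specialty: "For gynaecology consultants please base your answers on a trainee who is undertaking the following ATSM". The list names advanced laparoscopy and open and laparoscopic benign abdomen, and ends with "gynae-oncology and other sub specialty trainees involving major laparoscopic work".
- **Appendix 2, item 8 (trainees).** Respondents are asked for their expectations "of required laparoscopic abilities of trainees at CCT? Please mark your answer with an 'X". No reference trainee is described for O&G respondents.
- **Appendix 2, items 1 to 7.** The background items include grade ("Which level of training are you currently") but nothing on module, special interest or pathway.
- **Who receives the trainee form.** Under Study Protocol: "A short questionnaire will be sent to trainees nationally via the RCOG and BSGE". No restriction by module is stated for part 1.
- **Part 2, by contrast.** The Study Population footnote takes O&G trainees in their final two years only if they are trainees "with gynaecology special interest, who are undertaking at least one gynaecology Advanced Training Skills Modules (ATSM").

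**The concern.** The protocol treats pathway as material in O&G. Its background section says that intensive surgical training in the last two years goes only to trainees on a gynaecological pathway, and the part 2 eligibility rule acts on that. An O&G trainee at CCT in general and an O&G trainee on a laparoscopic module are therefore not the same person to rate.

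If consultants rate the second and some trainees rate the first, the two sets of answers are not about the same subject. A gap could appear where expectations agree, or a real gap could be hidden. What is at stake is the O&G half of the hypothesised discrepancy. The wording of the item and the variables collected are fixed in the questionnaires, so this is not a detail that can be left to an analysis plan.

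**Working it through.** The protocol gives no figure to reproduce for this comparison, so the check sets the two forms side by side.

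| Feature of the expectations block | Appendix 1, O&G consultants | Appendix 2 item 8, O&G trainees |
|---|---|---|
| Question | Expected laparoscopic abilities at CCT | Same |
| Scale | 1 to 5, disagreement to agreement | Same |
| Abilities listed | 10 | The same 10 |
| Trainee to be rated | On one of 3 named modules, or other sub-specialty training with major laparoscopic work | Trainees at CCT, not further described |

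Only the last row differs.

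**Is general surgery affected?** No. Neither form gives general surgery respondents a reference trainee, so the wording matches.

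**Which items are exposed?** All 10 expectations items, in 1 of 2 specialties. The 10 own-confidence items are not exposed, because each respondent rates themselves. Appendix 1 repeats the instruction in its block on experience of trainees, but Appendix 2 has no such block, so no consultant-trainee comparison arises there.

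**Can the responses be sorted afterwards?** The seven background items in Appendix 2 are gender, specialty, enrolment, training deanery, grade, start year and employing deanery. None of the 7 records pathway. Grade can isolate ST6/ST7 respondents, but those mix pathways, and grade does not show which trainee the respondent had in mind. Returns are anonymous (Data storage section), so nobody can be asked later.

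**Does the part 2 rule supply the missing definition?** No. It governs volunteers for the laparoscopic tasks, not survey respondents. Its list also differs: it names 5 modules, including urogynaecology and reproductive medicine, which the Appendix 1 instruction does not name.

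**How large could the effect be?** It depends on how many O&G trainees think of a trainee outside the Appendix 1 definition, and on how far ratings of the two kinds of trainee differ. The protocol gives neither. If every O&G trainee happens to think of a trainee within the definition, the effect is zero. A larger sample would not remove it.

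**The case against.** **The contrast is a small part of the study.** This stands. It is half of one hypothesis statement. It is not among the three numbered objectives, and the listed survey outcome concerns consultants' views. That limits the weight of the point, not its truth.

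**Other material may define the trainee.** The protocol says "The email accompanying the questionnaires will contain a brief introduction to the study", with an information sheet attached. Neither text is at hand, so the point is established for the forms only. Consultants also receive a covering email and information sheet, yet their definition was put in the question itself.

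**Recruitment through the BSGE may draw trainees who already think in laparoscopic terms.** Possibly, but the RCOG is used too, and the form cannot verify it.

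Three stronger readings are tempting, and the protocol does not support them.

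- *The consultant side is also ambiguous.* The specialty boxes separate "Gynaecology only" from the combined specialty, so a reader might infer that the second group is not addressed by the instruction. But Objective 3 uses gynaecological consultants for the whole side that is not general surgery, and the recruitment text calls the same people O&G consultants. The natural reading is that the instruction covers both boxes.
- *A difference between specialties in the gap would be an artefact.* The hypothesis is stated within each specialty, and no objective or outcome compares the gaps between specialties.
- *Consultants will look more demanding.* That direction is a guess: the protocol has no ratings by pathway and cannot show whom trainees had in mind.

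**Conclusion.** The point holds as a minor one. Appendix 1 and Appendix 2 item 8 define the rated trainee differently for O&G and are otherwise the same question. The O&G consultant-trainee comparison is therefore exposed to a mismatch in who is rated, and later analysis of anonymous returns can address this only in part.

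This is exposure, not demonstrated bias: the size and sign cannot be derived from the protocol, and the effect may be zero. The conclusion rests on the questionnaires as printed and assumes that the covering email and information sheet do not give trainees the same instruction.

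Objective 3 compares consultants with consultants and is unaffected. So are the listed outcomes, the general surgery half of the hypothesis, the own-confidence items and all of part 2.

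**What to change.** 1. In Appendix 2 item 8, add for O&G respondents the same reference-trainee sentence that Appendix 1 gives to gynaecology consultants. Use the Appendix 1 list, not the five-module list in the Study Population footnote.
2. Record which version of the form each response used.
3. Base the O&G consultant-trainee expectations comparison on trainee responses to the revised form. Retain all O&G consultant responses.
4. If the form cannot be changed, or wherever trainee responses to the unrevised form are used, report that O&G comparison as not like-for-like. Results for ST6/ST7 respondents (item 5) may be shown, as a partial check only.

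**Cost.** This is a one-sentence amendment to a survey that the timeline lists as ongoing from mid April 2021. There will be fewer usable O&G trainee responses for this one comparison, by a number the protocol does not allow to be estimated. Responses to the unrevised form keep every other use. Because returns are anonymous, there is a small risk that some trainees answer both versions. Step 4 needs no change to the form.

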We postulate that there is a difference in acquisition of fundamental laparoscopic skills (FLS) between general surgical and O&G trainees. This is likely to be demonstrated as a difference in musculoskeletal and cognitive fatigue between the specialties.

Within both specialties, there is likely to be a discrepancy in the expectations of consultants and trainees on skills perceived to be important at CCT.

Overall Aim

To compare and evaluate the training programmes in O&G and GS in order to identify areas for improvement in the training pathway contributing to the acquisition of FLS in both specialties.

Objectives

- 1) To compare FLS in O&G and GS trainees at ST3/4/5 and those in their final 2 years [ST7/8(GS) and ST6/7 (O&G)]
- 2) To compare the musculoskeletal and cognitive fatigue experienced by O&G and GS trainees in performing FLS as a marker of their competence.
- 3) To compare the standards of laparoscopic ability expected from trainees by experienced GS and gynaecological consultants.

Research Strategy

Study Design

This is a prospective comparative study and we will recruit participants from professional membership bodies and the North West health education formerly known as the North West deanery. The study is divided in two parts. In part 1, Consultants and trainees from O&G and GS specialties will be contacted electronically through professional membership bodies (O&G consultants through RCOG/BSGE, GS consultants through ASGBI, O&G trainees through RCOG/BSGE and GS trainees through ASiT). In addition to above communication methods we will consider the use of social media and direct emails to increase survey response rate. The consultants and trainees will be requested to fill out an online short questionnaire designed to assess their perceptions of FLS required at CCT (Appendix 1& 2). These surveys will not include any personal details and will be returned anonymously to us via the survey monkey platform. In the second part we will recruit trainees from the two specialties via the North West deanery by sending out a centralised email requesting them to volunteer for the

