- Task 1 is ideally completed in 2 minutes and 30 seconds, however trainees will not be confined to this time and will be allowed to continue until all 14 targets have been identified or reached 5 minutes. The rationale for putting a time limit of 5 minutes per round is to avoid fatigue. We will record the time taken (in minutes and seconds) to locate the 14 targets and will average this across 3 rounds. If the task is incomplete by 5 minutes, we will record the last found target (small character). Those trainees who are able to complete the task but have taken longer than 2 minutes and 30 seconds will incur a penalty. For every 30 seconds exceeded beyond 2 minutes and 30 seconds we will subtract 1 target from the total number of targets they have found.
- For tasks 2-3, we will record the time taken in minutes and seconds to complete the tasks and use an average of this across 3 rounds. If the tasks are not completed within time (i.e. 3 minutes) then we will record the number of objects handled within 3 minutes and take an average of this across 3 rounds. Where participant shows mixed/inconsistent performance (i.e. completes the task once in time (i.e. 3 minutes) but not on the other two runs then we will use the average number of handled objects over 3 runs and note the performance as mixed/inconsistent. If an object is dropped whilst being handled, the number of drops will be recorded as this indicates inefficient performance.
- For task 4 the number of sutures, correct knots and extent of trauma will be recorded on the evaluation sheet and maximum time allowed will be 15 minutes.

Secondary outcome measures:

- EMG and EEG signal analysis.
- Qualitative measures such as consultant's perception of trainee's laparoscopic ability and the abilities they regard as important at CCT using a likert scale of 1-5.

Regulatory issues

Consent

The research team responsible for conducting the study are trained medical practitioners and are able to assess capacity and take informed consent.

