Proficient in use of laparoscopic staplers					

What is your experience of laparoscopic abilities of trainees at CCT? For gynaecology consultants please base your answers on a trainee who is undertaking the following ATSM: Advanced laparoscopy, open and laparoscopic benign abdomen, gynae-oncology and other sub specialty trainees involving major laparoscopic work. Please mark your answer with an 'X'

Strongly Disagree – 1, Disagree -2, Neither agree nor disagree-3, Agree -4 and Strongly agree – 5.

Laparoscopic ability	1	2	3	4	5
Proficient in obtaining laparoscopic intra-abdominal access					
Proficient in recognition of anatomy and anatomic tissue planes laparoscopically					
Proficient in safe manipulation of tissue laparoscopically					
Proficient in dissection of tissue planes laparoscopically					
Able to control bleeding laparoscopically using diathermy/energy devices.					
Able to control bleeding laparoscopically using endovascular staplers/haemolocks/endoloops					
Able to control bleeding laparoscopically using haemostatic agents ie Flowseal/surgicel					
Proficient in appropriate use of laparoscopic energy devices					
Proficient in laparoscopic suturing					
Proficient in use of laparoscopic staplers					

How would you rate your own confidence with the listed laparoscopic skills? Please mark your answer with an 'X'

Not at all confident -1, Not so confident-2, Somewhat confident -3, Very confident -4, extremely confident-5.

Laparoscopic ability	1	2	3	4	5
Proficient in obtaining laparoscopic intra-abdominal access					
Proficient in recognition of anatomy and anatomic tissue planes laparoscopically					
Proficient in safe manipulation of tissue laparoscopically					
Proficient in dissection of tissue planes laparoscopically					
Able to control bleeding laparoscopically using diathermy/energy devices.					
Able to control bleeding laparoscopically using endovascular staplers/haemolocks/endoloops					
Able to control bleeding laparoscopically using haemostatic agents ie Flowseal/surgicel					
Proficient in appropriate use of laparoscopic energy devices					
Proficient in laparoscopic suturing					
Proficient in use of laparoscopic staplers					

Appendix 2

Trainee Questionnaire: Expectations of Fundamental Laparoscopic Skills Required by the end of Higher Specialty Training and current level of confidence.

1. Gender

	Mark with 'X'			Mark with 'X'		Mark with 'X'

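### Appendix 1 gives gynaecology consultants a laparoscopy-track reference trainee but gives general surgery consultants none, so the consultant comparison between specialties partly depends on the form's wording

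*Protocol*

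**What the plan says.** Objective 3 reads "To compare the standards of laparoscopic ability expected from trainees by experienced GS and gynaecological consultants". The secondary outcome measures include "consultant's perception of trainee's laparoscopic ability and the abilities they regard as important at CCT using a likert scale of 1-5".

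Appendix 1, the consultant questionnaire, has two grids in which consultants rate trainees:

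- The expectations grid opens with "What are your expectations of required laparoscopic abilities of trainees at CCT".
- The experience grid opens with "What is your experience of laparoscopic abilities of trainees at CCT".

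Both openings are common to the two specialties. In each grid they are followed by an instruction for gynaecology consultants alone: "For gynaecology consultants please base your answers on a trainee who is undertaking the following ATSM: Advanced laparoscopy, open and laparoscopic benign abdomen", continuing with "gynae-oncology and other sub specialty trainees involving major laparoscopic work". No matching instruction for GS consultants appears in either grid. A third grid asks consultants about their own confidence; it needs no reference trainee and is not affected.

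**The concern.** A comparison of standards between two groups of raters needs both groups to be rating a comparably defined person. Here the form defines that person for one group and leaves it open for the other. If GS consultants picture a broader range of trainees than the gynaecology consultants are told to picture, the two sets of 1-5 ratings answer different questions.

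The interpretation of Objective 3 is at stake in the expectations grid, and the perception part of the secondary outcome in the experience grid. A gap between specialties could be read as a difference in standards, or similar ratings as agreement, when part of the result comes from the instruction. Analysis cannot repair this. Replies are anonymous, and Appendix 1 does not ask which trainee the consultant had in mind.

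**Working it through.** The protocol states no figure on this point, so there is none to reproduce. The check sets the relevant places side by side.

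1. **Who is rated, gynaecology side (Appendix 1, both grids).** A trainee on the advanced laparoscopy, benign abdomen or gynae-oncology modules, or in other sub-specialty training with major laparoscopic work.

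2. **Who is rated, GS side (Appendix 1, both grids).** Trainees at CCT, with nothing further. The specialty question offers GS respondents one box, Colorectal/HPB/Upper GI. That box describes the consultant, not the trainee. Gynaecology consultants also tick a specialty box, yet for them the form still specifies the trainee.

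3. **Why gynaecology is restricted at all.** The background says that the first five O&G years are largely obstetric and that only the gynaecology pathway brings intensive surgical training, in the last two years. The inclusion criteria for Part 2 restrict senior O&G recruits to those on at least one gynaecology ATSM, because O&G covers two curricula. That reason is written for Part 2 and not repeated for the survey, but it carries over.

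4. **Whether the Appendix 1 restriction is the same one.** It is not. The Part 2 list also names urogynaecology and reproductive medicine. Appendix 1 names neither; such trainees could enter only through the catch-all, which requires major laparoscopic work. The Part 2 rule selects the gynaecology track. The Appendix 1 rule also selects on the amount of laparoscopic work.

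5. **What this does to the contrast.** Write G(r) and O(r) for the mean ratings that GS and gynaecology consultants would give to a reference trainee of type r in their own specialty, with u = unspecified and l = laparoscopy track. The form estimates G(u) − O(l), which splits as

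   G(u) − O(l) = [G(l) − O(l)] + [G(u) − G(l)].

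   The first bracket is the like-for-like contrast. The second is the wording effect, and it lies wholly on the GS side. It is zero if GS consultants picture a laparoscopy-track trainee without being told to. The protocol gives no rating distribution and no account of whom GS consultants would picture, so the second bracket has no value and no sign that can be derived from it.

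6. **Which outcome each grid serves.** The expectations grid matches Objective 3, which concerns expected standards. The experience grid matches the perception part of the secondary outcome and is not strictly an Objective 3 measure.

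**The case against.** The strongest reply is that the instruction makes the two sides more alike. Without it, a gynaecology consultant might rate an obstetric-track trainee with little operative laparoscopy, which would be a poor counterpart to a GS trainee. That stands, and it is why the gynaecology frame should be kept. It does not explain why the frame goes beyond being on the gynaecology track, or why GS has no counterpart.

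A second reply is that GS respondents are colorectal, HPB or upper GI consultants and will think of trainees in those areas. This is probable, so it would be wrong to call the GS reference trainee unselected. It is undefined.

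A reader might also infer that the frame lifts the gynaecology ratings by a calculable amount: if a share p of O&G trainees fit the frame and are rated d points above the rest, the lift is (1 − p) × d. The documents give neither p nor d. More importantly, that product is O(l) minus the mean for all O&G trainees, obstetric track included. It counts as bias only if all O&G trainees are the right comparator, which the protocol's own reasoning argues against. It does not measure G(u) − G(l).

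Nor do the documents support reading the frame as shrinking or reversing a true gap in favour of GS. The background states a belief that GS trainees have earlier and greater laparoscopic exposure. It says nothing about which consultants hold higher standards, and the hypothesis gives no direction.

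**Conclusion.** The point holds as a defect in the instrument: one specialty's reference trainee is specified and partly selected on laparoscopic intensity, while the other's is left open, in both grids. The GS-versus-gynaecology result is conditional on that wording. Its effect on the ratings could be small if GS consultants already picture trainees in laparoscopic sub-specialties; the documents fix neither size nor direction.

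The consequence is limited to Objective 3 and a secondary outcome. The primary task outcomes are untouched. It is still worth correcting, because a stated objective rests on this comparison and the ambiguity cannot be removed once anonymous replies are in.

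**What to change.** Keep the gynaecology instruction and add a parallel sentence for GS consultants to both grids, for example: *For general surgery consultants, please base your answers on a trainee in colorectal, HPB or upper GI sub-specialty training involving major laparoscopic work.* Record which version of the form each reply used, since the study timeline shows Part 1 open from mid April 2021 and ongoing.

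The change is one sentence in two grids of an online form. The real cost is that replies before and after it must be analysed separately, and form version is then tied to response date, so a difference between versions could not be put down to wording alone.

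If collection is complete, or the form is left as it is, state the frames in the conclusion: laparoscopy-track (ATSM or sub-specialty) gynaecology trainees versus GS trainees at CCT with no reference trainee specified, as rated by Colorectal/HPB/Upper GI consultants. This costs nothing but narrows what can be claimed.
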